The existing research on lactic acid-containing gel is promising. Of all studied methods of vaginal delivery of lactic-acid, including a douching system, a slow-release delivery pessary, lactic acid capsules, and a lactic acid-containing gel, the lactic acid-containing gel seems to be most effective. One study shows that the use of lactic acid gel as a treatment for bacterial vaginosis is comparable, but not superior to, the use of metronidazole^{8,9,10}. Currently, no research has been done on lactic acid gel as a prophylactic agent for patients who suffer from recurrent BV and/or yeast infections. This study aims to explore the feasibility and efficacy of a lactic acid-containing gel as prophylaxis against recurrent BV/yeast infections.

While several studies have been done which suggest that, as a treatment, intravaginal lactic acid gel is non-inferior to metronidazole, there have been no studies which explore its potential as a preventative agent. Compared to antibiotic therapies, lactic acid supplementation may be a more cost effective way to prevent BV and/or yeast infections, thereby reducing morbidities related to these conditions in patients who suffer from recurrent infections.

Section II: Criteria for Subject Selection

1. Number of subjects:

We will enroll a total of 22 patients. Using the Viechtbauer et al. method for calculating sample size in pilot studies¹¹, with a confidence level of 95% and probability of error prevalence estimated to at least 15%, the recommended sample size is 20. To account for exclusions and drop outs (estimated to be 10%), we should enroll a total of 22 patients.

2. Demographics of subjects:

Patients who undergo screening and are found to meet inclusion criteria will be invited to participate in this study.

Inclusion criteria

- Age 18-54
- Female
- Pre-menopausal
- Can speak and read in English
- Displays capacity for informed consent
- Has had 2 or more documented and/or self-reported episodes of symptomatic BV or candida infection in the last year, requiring, over-the-counter or prescription treatment

Exclusion criteria

- Pregnant or trying to become pregnant
- Post-menopausal
- Using NuvaRing device
- A past medical history of kidney disease, recurrent UTI, and/or urinary tract abnormalities
- Current UTI
- Using Phexxi as a contraceptive during the collection period of the study

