*Note: NuvaRing is the only medication that will be included in the exclusion criteria. While we will ask all participants to provide a list of medical conditions they have and a list of medications they are currently taking, these will be for the purposes of data analysis, and to account for possible confounders of our data.

*Note: patients do not have to be symptom-free to participate in this study. However, as stated below, if they receive antibiotic/antifungal treatment prior to starting the study, we will ask them to wait 10 days after the completion of the treatment before they collect their first swab, in order to allow for the restoration of their baseline bacterial flora.

3. Vulnerable subjects:

N/A. Pregnancy is listed as an exclusion criteria, and no minors or incarcerated persons will be included in this study.

Section III: Methods and Procedures

1. Study design and methods

This is a single center, prospective trial, which comprises of a pre-post study design will be looking at the vaginal microbiome makeup of participants before and after a four-week course of Phexxi. The primary outcomes will be an increase in lactic acid-forming lactobacilli, as well as a decrease in patient-reported symptoms of vulvovaginitis.

This study will be based at the Queen's Medical Center (QMC), [name]. Eligible patients will be approached by participating clinicians (all doctors providing care at the 1004 clinic, as delineated in the LOA form) to assess interest in study participation.. The principal investigator will review the weekly schedule for the 1004 clinic and alert the attending physicians of patients who may be eligible for the study based on chart review. A HIPAA waiver will be required for this stage of recruitment, as the principal investigator would otherwise not be accessing these patient's charts. The attending physician staffing the 1004 clinic will ask the flagged patients if they are interested in learning about the study and review general study objectives with patients. If the patient is interested in participating, the research associates will approach the patient to more thoroughly screen, then conduct the informed consent process. Informed consent will be collected from every participant prior to the start of the study.

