The intervention will take place on a rolling basis, as patient participation will have no bearing on other participants. The intervention itself will take place over thirty days. 8 pre-filled vaginal inserters with vaginal gel, will be provided to each of the participants with verbal and written instructions for application. Patients will be instructed to use Phexxi twice per week, on the same days every week. Throughout the 30 days, participants will also be asked to keep a diary of events (Appendix E) occurring when they used the product, such as intercourse or menses, as well as record any symptoms or side effects they noticed when using the product. The diary can be sent back with the second specimen vial. Disposal of the product may be done in a regular waste basket.

Approximately 30 days after completion of the intervention, participants will receive an email reminder to collect and send a third collection swab in (Appendix G) for analysis. This email will also include the link for the third and final set of surveys (B and C).

2. Data analysis and monitoring (include adverse event reporting procedures)

The pre-and post-intervention results will be compared with the subjects to serve as their own controls in this pilot study. To assess for the primary outcomes, each bacteria identified in the NextGen analyses of the composition of the pre-intervention microbiome sampling will be individually named, then classified as either “lactic acid-forming (LAF)” or “not lactic acid-forming (NLF)”. This will allow us to identify which CST each participant falls under prior to the study, and to assess if they can be classified under a different CST at the end of the study. It also allows us to conduct an independent t-test to test for significance between two variables (LAF/NLF) pre and post-intervention.

Demographic data will be collected from patient surveys. Demographic information to be collected will include age, ethnicity, number of reported vaginal yeast infections or BV infections in the last year, type of contraception used, type of diet, and medical comorbidities/current medications. This demographic information will allow us to perform a multiple regression analysis on our data set to account for confounding factors in our study population.

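### The sample size of 20 rests on problem detection and does not bear on the primary pre-post changes, one of which is then tested with an independent t-test although each woman is her own control

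*Protocol*

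**What the plan says.** Section II.1 (Number of subjects) states "We will enroll a total of 22 patients". It cites a "method for calculating sample size in pilot studies", and its only inputs are these: "with a confidence level of 95% and probability of error prevalence estimated to at least 15%, the recommended sample size is 20". The step from 20 to 22 is a loss allowance: "To account for exclusions and drop outs (estimated to be 10%), we should enroll a total of 22 patients". The section gives no effect size, standard deviation, significance level, power or target precision. It does not say which problem the 15% refers to.

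Section III.1 (Study design and methods) defines what the trial is to show: "The primary outcomes will be an increase in lactic acid-forming lactobacilli, as well as a decrease in patient-reported symptoms of vulvovaginitis".

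Section III.2 (Data analysis and monitoring) sets out the comparison: "The pre-and post-intervention results will be compared with the subjects to serve as their own controls in this pilot study". In the same paragraph it says that the team will "conduct an independent t-test to test for significance between two variables (LAF/NLF) pre and post-intervention". It names no test for the symptom outcome.

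**The concern.** Two things do not fit together.

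First, the stated basis for the number of women concerns how likely a problem is to come to light. The primary outcomes are changes within women. Nothing in Section II.1 tells the reader how large a change 20 women could reveal, or how precisely it would be estimated.

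Second, the one test that is named treats the before and after values as coming from separate groups, while the same paragraph makes each woman her own control. If a woman's two values are positively correlated, that test uses too large a standard error and gives away much of the information in a small sample.

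What is at stake is the meaning of a null result. A small study analysed with a test that ignores pairing can easily miss a real change in lactobacilli. The protocol offers no figure that would warn against taking non-significance as evidence that the gel has no effect.

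**Working it through.** **Inputs from the protocol.** Confidence 95%, problem prevalence 15%, recommended size 20, loss 10%, enrolment 22 (all Section II.1); pre-post design with women as own controls, and independent t-test (Section III.2).

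**Assumed, because the protocol gives none.** Two-sided 5% level, 80% power as benchmark, pre-post correlation ρ from 0 to 0.7, roughly normal values with equal variance before and after. The named test is taken to compare 20 pre with 20 post values.

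**1. Reproducing the stated 20.** If the aim is to see a problem of prevalence p at least once with probability γ, then n = ln(1 − γ)/ln(1 − p).
- ln(0.05)/ln(0.85) = 18.4, so 19.
- With 19 women: 1 − 0.85^19 = 0.954. With 20: 1 − 0.85^20 = 0.961. With all 22 enrolled: 1 − 0.85^22 = 0.972.

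The stated 20 is one above the computed 19 and meets the 95% target. The protocol does not spell out this reading; it is inferred because the two inputs lead to nearly the stated number.

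**2. Loss allowance.** 20 × 1.10 = 22 as stated. Dividing instead gives 20/0.90 = 22.2, so 23; and 22 × 0.90 = 19.8. The difference is one woman and is not pursued.

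**3. What 20 complete pairs give on the primary outcomes, analysed as pairs.**
- Precision: half-width of the 95% CI = t(0.975; 19)/√20 = 2.093/4.472 = 0.47 SD of the within-woman change.
- Detectable change: from the noncentral t distribution with 19 degrees of freedom and noncentrality d√20, power is 80% at d = 0.66. With 18 pairs it is 80% at d = 0.70.
- Power with 20 pairs: 25% at d = 0.3, 56% at d = 0.5, 92% at d = 0.8.
- On the scale of the raw SD, 0.66 × √(2(1 − ρ)) gives 0.93, 0.78, 0.66 and 0.51 for ρ = 0, 0.3, 0.5 and 0.7.

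Neither the 95% confidence nor the 15% prevalence enters any of these lines.

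**4. What the independent t-test does to the same data.** It takes the variance of the mean change as 2σ²/n, whereas for paired values it is 2σ²(1 − ρ)/n. The test statistic is therefore shrunk by about √(1 − ρ), which is 0.71 at ρ = 0.5. Simulation with 20 bivariate normal pairs (400,000 replicates), nominal two-sided 5%, true change 0.66 SD of the differences:

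| ρ | Type I error, independent | Power, independent | Power, paired |
|---|---|---|---|
| 0 | 5.0% | 82% | 80% |
| 0.3 | 2.1% | 70% | 80% |
| 0.5 | under 1% (about 0.7 to 0.8%) | 54% | 80% |
| 0.7 | 0.1% | 27% | 80% |

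The paired test holds its 5% level throughout. The loss from the independent test grows quickly with correlation and is absent only when a woman's two values are unrelated.

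**The case against.** The strongest reply is that this is a pilot, sized by a pilot formula and called a pilot again in Section III.2. Formal power is not obligatory, no sentence claims it, and the stated 20 reproduces closely. All of that stands.

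A reader might infer more than the document supports in five ways:
- **That 20 is a miscalculation.** It is not; it delivers slightly more than the 95% sought.
- **That the number answers a question the trial never asks.** Section I.3 gives feasibility as an aim alongside efficacy. Appendix D includes a feasibility measure, the diary in Appendix E records use and side effects, and Section IV.3 requires side-effect withdrawals to be reported. The narrower point is that the 15% problem is not identified and that feasibility is not a primary outcome.
- **That both primary outcomes are significance tests.** A test is named only for the LAF/NLF outcome. The symptom outcome is also a pre-post change, but its analysis is left open, which is no finding while an analysis plan may exist.
- **That more women are needed.** Nothing here requires that. A pilot may estimate imprecisely, provided the imprecision is stated.
- **That the independent test risks false positives.** Under positive correlation it errs the other way, towards missing a real change.

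It can also be said that reporting estimates with intervals is commonly left to an analysis plan. That is fair for presentation in general. The independent t-test, however, is written into this protocol, beside a sentence that contradicts it. How readers would interpret a null result is a risk and not something the documents show.

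**Conclusion.** The point holds in a limited form. The basis for the sample size is sound for detecting problems and silent on the outcomes called primary. By itself that calls for clarification and would change no result.

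The part that can change a result is the test. Section III.2 contradicts itself by using women as their own controls and then applying an independent t-test. At an assumed correlation of 0.5, this turns 80% power into about 54% and a nominal 5% level into less than 1%. Even with the correct paired analysis, a true change of half an SD would be missed about 44% of the time (100% − 56%), so non-significance cannot be read as no effect.

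The precision and power figures rest on a two-sided 5% level and 20 complete pairs. The comparison of tests rests also on the unknown pre-post correlation and on approximate normality, which sequencing-based measures may not meet without transformation.

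**What to change.** Keep enrolment at 22.

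**Section III.2:** replace the independent t-test with the within-woman change from before to after the intervention. Report its mean and 95% CI from a paired analysis as the primary result, and add that a non-significant result is not evidence of no effect.

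**Section II.1:** add wording such as this: *The number enrolled rests on problem detection. Among 22 women enrolled there is about a 97% chance (96% among 20) of observing at least one case of a problem that affects 15% of women. The primary outcomes are not powered. With 20 complete pairs the 95% CI for a mean change extends about 0.47 SD of the paired change either side, and 80% power is reached only for a change of about 0.66 SD (two-sided 5%).* The study team should also name the problem to which the 15% refers. If that problem is non-completion, the denominator has to be the women enrolled, since completers cannot show it.

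**Cost:** a few sentences and one change of test, with no further women, samples or visits. The drawback is that the stated justification looks less favourable.

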After obtaining informed consent, the research team will review standardized instructions for using the study medication with the patient and the research associate will provide a take-home kit including all of the study materials, including instructions for collecting each swab (Appendix A) and for returning the samples. Samples will be self-collected by participants at their home at intervals specified in the study instructions. All materials provided to the patient will be pre-labeled with their study ID, protecting each participant's PHI. No collections will take place in-clinic. These materials include all surveys, patient's diary, and all swab vials.

All vaginal swabs must be frozen within 48 hours of collection. As such, the participants will be asked to send their samples within 24 hours in order to give adequate time for delivery to the storage facility and be asked to collect their specimens between Sunday and Thursday so samples can reach the facility during business hours. Freezing will occur at the research site. Each patient's study kit will include a prepaid shipping envelope, which the participant can use to mail or drive their specimen to the research team who will then place it in the freezer until it is ready for analysis.

The first phase of the study will include an assessment and classification of patients' vaginal microbiome prior to receipt of the intervention. To get the best representation of the participant's baseline microbiome, the participant will be asked to collect their baseline swab no sooner than 10 days after menses, as menses-induced changes in the microbiome have been shown to resolve after this time¹². For similar reasons, if participants are being treated with an acute course of antibiotics or antifungals at the time of recruitment, they will be asked to wait 10 days after the completion of their medication course before collecting their baseline swab. There will be two additional time points for collection: collection 2) at the end of the 30 day intervention, and collection 3) 30 days after completion of the intervention.

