Appendix B Patient demographic survey

Demographic Survey

Subject ID:

1: What is your age?:

2: What is your race?

3. Are you Hispanic/Latinx?

4.: How many yeast infections or episodes of bacterial vaginosis (BV) have you had in the last year?

5: Are you on any kind of birth control? If yes, what kind?

6: In the next portion, please describe what kinds of food you normally eat in a typical day. In addition to meals, please include snacks. If you are currently on a specific type of diet, please state that here.

Breakfast

Lunch

Dinner

Other

7 What other medical conditions have you been diagnosed with? If none, please write, "none".

8: Please list any medications/supplements you are currently taking. If none, please write, "none".

Appendix C. Survey to assess vulvovaginitis symptoms. Modified version of the Vulvovaginitis Symptom Questionnaire (VSQ)

During the past week, have you been bothered by:

1. Your vulva itching? 0 No 1 Yes

2. Your vulva burning or stinging? 0 No 1 Yes

3. Your vulva hurting? 0 No 1 Yes

4. Your vulva being irritated? 0 No 1 Yes

5. Your vulva being dry? 0 No 1 Yes

6. Discharge from your vulva or vagina? 0 No 1 Yes

7. Odor from your vulva or vagina? 0 No 1 Yes

8. Worry about your vulvar symptoms? (for example, that it will spread, get worse, scar, etc.) 0 No 1 Yes

9. The appearance of your vulva? 0 No 1 Yes

10. Frustration about your vulvar symptoms? 0 No 1 Yes

11. Embarrassment about your vulvar symptoms? 0 No 1 Yes

- 12. The effects of your vulvar symptoms on your interactions with others? 0 No 1 Yes
- 13. The effects of your vulvar symptoms on your desire to be with people? 0 No 1 Yes
- 14. Your vulvar symptoms making it hard to show affection? 0 No 1 Yes
- 15. The effects of your vulvar symptoms on your daily activities? 0 No 1 Yes
- 16. Your vulvar symptoms affecting your desire to be intimate? 0 No 1 Yes
- 17. Are you currently sexually active with a partner?
 No → Thank you. You are done with this questionnaire. Yes → Please proceed with the next 4 questions
- 18. The effects of your vulvar symptoms on your sexual relationships? 0 No 1 Yes
- 19. Your vulvar symptoms causing pain during sexual activity? 0 No 1 Yes
- 20. Your vulvar symptoms causing dryness during sexual activity? 0 No 1 Yes
- 21. Your vulvar symptoms causing bleeding during sexual activity? 0 No 1 Yes

Please use the space below to list any vulvar/vaginal symptoms you are experiencing which have not already been listed.

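### Recent Phexxi use and other vaginal lactic-acid products fall outside the exclusion and the pre-baseline waits, so any such woman who enrols may give a partly treated baseline swab

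*Protocol*

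**What the plan says.** **Eligibility.** Section II.2 has one criterion on Phexxi outside the study: "Using Phexxi as a contraceptive during the collection period of the study". No criterion mentions any other vaginal lactic-acid product. The note after the list says that "NuvaRing is the only medication that will be included in the exclusion criteria". Other medications are to be listed, and "these will be for the purposes of data analysis, and to account for possible confounders of our data".

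**Timing of the baseline swab.** Section III.1 describes the first phase as an "assessment and classification of patients' vaginal microbiome prior to receipt of the intervention". Two waiting rules protect it. Participants are to "collect their baseline swab no sooner than 10 days after menses", and those on an acute antibiotic or antifungal course are to "wait 10 days after the completion of their medication course before collecting their baseline swab". The second note in Section II.2 repeats the antibiotic and antifungal rule. No wait is set for a lactic-acid product.

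**Records.** Appendix B asks for the current type of birth control and then: "Please list any medications/supplements you are currently taking". The Appendix E diary, kept during the 30-day intervention, gives new medications as one example of an event to note.

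**Comparison.** Section III.2 states: "The pre-and post-intervention results will be compared with the subjects to serve as their own controls in this pilot study". There is no concurrent control group.

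**The concern.** The trial asks whether adding lactic acid to the vagina shifts the flora toward lactic-acid-forming bacteria. The answer rests on one contrast within each woman, before against after. Section III.1 takes care that menses and anti-infective drugs do not distort the first sample, but it sets no equivalent rule for the exposure under test.

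On the protocol's own hypothesis, a woman who has recently put lactic acid into the vagina may start with more lactic-acid-forming bacteria than she would otherwise have. Her change after study treatment would then be too small. If she is not identified, she can be neither set aside in a sensitivity analysis nor adjusted for. Use of another such product after baseline would also blur what collections 2 and 3 can be credited to.

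**Working it through.** **Step 1. Set the rules against the possible exposures.** The protocol does not define the collection period. I take it to run from the baseline swab to collection 3.

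| Exposure | Excluded? | Wait before baseline? | Asked about? |
|---|---|---|---|
| Phexxi for contraception, from baseline on | Yes | Not needed | Yes, birth control item |
| Phexxi for contraception, stopped before baseline | No | None | No |
| Phexxi for another purpose, outside the study | No | None | Only if current and listed as a medication |
| Another vaginal lactic-acid product, current | No | None | Only if listed as a medication or supplement |
| Another vaginal lactic-acid product, recently stopped | No | None | No |
| Antibiotic or antifungal course | No | 10 days | If current |

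Rows two to five are the gap. It follows from the criterion as written, so it is not a detail left to an analysis plan.

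**Step 2. Planned numbers.** Section II.1 uses 95% confidence and a 15% problem probability. The pilot formula gives n = ln(1 − 0.95)/ln(1 − 0.15) = 18.43, rounded up to 19; the protocol states 20. Adding 10% gives 20 × 1.10 = 22, as stated. This point does not depend on the difference of one. I use 20 evaluable and 22 enrolled women.

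**Step 3. Dilution (illustration).** Let δ be the mean change in unexposed women. Suppose k of 20 women have an exposed baseline and keep a fraction r of that change. Then

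mean change = δ × [1 − (k/20)(1 − r)].

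In the extreme case r = 0 (no further change), the fall is k/20:

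- k = 1: 5%
- k = 2: 10%
- k = 4: 20%
- k = 6: 30%

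With r = 0.5 each figure halves; for k = 4 the fall is (4/20)(0.5) = 10%. The protocol gives neither k nor r.

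**Step 4. Chance that it arises at all (illustration).** If a proportion p of eligible women are exposed, the chance of at least one among 22 is 1 − (1 − p)^22:

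- p = 1%: 20%
- p = 5%: 68%
- p = 10%: 90%
- p = 20%: 99%

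Again, p is assumed. I give no effect on power, because that would also need an effect size that the protocol does not state.

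**Step 5. Direction.** Exposure before baseline biases the change toward zero if the hypothesis is true. A product first used between baseline and collection 2 would act the other way, because its effect would be credited to the study gel.

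**The case against.** **Such women may be rare.** Section I.2 says Phexxi is approved as a contraceptive and that its other uses are under study, so excluding contraceptive use covers its approved use. The criterion's wording may only be meant to separate outside use from the study applicators. For Phexxi itself, the remaining gap is then mainly use stopped just before the first swab. Section I.3 lists lactic-acid douches, pessaries, capsules and gels as delivery methods that have been studied, not as products these patients buy. Over-the-counter treatment in the inclusion criterion may well mean antifungals, which already carry a wait. All this stands, and it limits how large the problem can be said to be.

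**Some users would be seen.** A reader might infer that nothing on file would reveal an exposed woman. The documents do not support that. Charts are reviewed before approach, eligibility is screened in person, Appendix B lists current products, and the diary prompts for new medications. A current user may well be recorded. What is not asked about is recent, stopped use. The planned multiple regression cannot adjust for what was not recorded, and with about 20 women it is weak even for what was.

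**The NuvaRing note may be loose wording.** It can be read as concerning participants' other medications, with Phexxi set apart as the study drug. That is a fair reading. Taken literally, though, it conflicts with the Phexxi criterion a few lines above, and an editorial correction settles it.

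**Conclusion.** The gap stands. Followed exactly, the criterion admits women recently exposed to the agent under test and women using another product with the same active principle, and the recently stopped user is not recorded. This runs against Section III.1's own effort to obtain a representative baseline, in a design where that swab is the only comparator.

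The bias is conditional. It needs such women to enrol, the hypothesis to be true, and some effect to last until the baseline swab. The documents support none of these with a figure, so the size is unknown. The fall of k/20 in mean change is an upper illustration that assumes no further change in every exposed woman.

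Two stronger readings are tempting and not supported:

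- A reader might infer that participants' baseline swabs are already exposed. The protocol shows only that the rules would allow it.
- A reader might infer from collection 3 that 30 days is the right washout. That is a time chosen for observation; nothing shows that an effect has gone by then.

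**What to change.** 1. **Section II.2, exclusion criterion.** Define it by source rather than purpose: any non-study use of Phexxi or of another intravaginal lactic-acid product, for any reason, from a stated interval before the baseline swab through collection 3. The sponsor should choose and justify the interval; none is proposed here. In Section III.1, defer the baseline swab until the interval has passed, in the same way as is already done after antibiotics and antifungals.
2. **Appendix B.** Add an item on vaginal products used recently, prescribed or not, with the date of last use.
3. **Section II.2, first note.** Reconcile the statement about NuvaRing with the Phexxi criterion.

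The cost is one criterion with its matching swab rule, one survey item and one corrected note. A few women would be deferred or excluded. Rolling entry makes deferral manageable, but women who rely on Phexxi for contraception would be affected earlier than under the present criterion, and the sponsor should weigh this when setting the interval.

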Once received at the research site, samples will be stored in a specimen freezer at -80 degrees F until all specimens are received, at which point they will analyzed using NextGen sequencing, a DNA sequencing technology that will identify the genetic makeup of their specimens. This will be done to sequence the genome of the bacteria of the microbiome, not the patient's genetic material. The first phase of the study will also include a survey (Appendix B), which will collect demographic information from each participant, as well as assess patients' current acceptability of a vaginal gel for prophylactic use, their most bothersome symptoms, and how their quality of life is affected by recurrent vulvovaginitis. The specific information collected from each

participant can be found below in Data Analysis. The survey used to measure this will be the **Vulvovaginal Symptom Questionnaire (VSQ)**, which has been validated for the purposes stated above (Appendix C). There will also be an added space in the survey provided for open-ended answers and comments.

Measurement for primary outcomes will be done using two separate methods. In order to assess for the presence of lactic acid-forming organisms before and after the lactic acid gel intervention, NextGen DNA sequencing will be completed on self-collected samples submitted by participants. The analysis of these samples will be performed by [name], at an in-house lab run by the UH Maternal Fetal Medicine division. In order to assess for patient-experienced symptoms, **survey B (Appendix C) will be administered prior to, immediately after, and 30 days after intervention.**

In order to measure our secondary outcome, Survey C (Appendix D) will be administered at collection points 2 and 3.

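### The stated aim is prophylaxis, but the symptom outcome is a fall from baseline in women who enter with or without symptoms, so a pooled fall cannot show prevention

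*Protocol*

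**What the plan says.** - **Aim.** Section I.3 (Preliminary studies) separates treatment, which it says has been studied, from prevention, which it says has not. It then states: "This study aims to explore the feasibility and efficacy of a lactic acid-containing gel as prophylaxis against recurrent BV/yeast infections".
- **Entry.** The disease criterion in Section II.2 is history alone: "Has had 2 or more documented and/or self-reported episodes of symptomatic BV or candida infection in the last year". A note to the criteria adds that "patients do not have to be symptom-free to participate in this study". Women given an antibiotic or antifungal before the start wait 10 days after the course before the baseline swab. No criterion concerns current status.
- **Outcome.** Section III.1: "The primary outcomes will be an increase in lactic acid-forming lactobacilli, as well as a decrease in patient-reported symptoms of vulvovaginitis". Section I.1 words the symptom outcome in the same direction. Recurrence is not named as an outcome.
- **Measurement.** Section III.1: "survey B (Appendix C) will be administered prior to, immediately after, and 30 days after intervention". The Appendix C items are scored 0 or 1 and open with "During the past week, have you been bothered by".
- **Analysis.** In Section III.2 each woman is her own control. A baseline community state type (CST) is assigned, and a multiple regression for confounders is planned. The factors listed for it do not include baseline symptom status.

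**The concern.** Two kinds of women enter, and they answer different questions. A woman with symptoms at baseline can show a fall, which speaks to the course of a current episode. A woman without symptoms can show prevention only by staying as she is, and an outcome defined as a decrease records that as no effect.

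The pooled symptom result therefore depends on how many women happen to enter with symptoms. A positive result could be reported as support for prophylaxis although no symptom-free woman contributed to it. A null result could be reported as failure although every symptom-free woman stayed well.

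**Working it through.** The protocol gives no expected effect, standard deviation or symptom-free share for Survey B, so there is no planned figure to reproduce. The inputs taken from it are 20 women after dropout (Section II.1), the 0/1 scoring (Appendix C) and BV recurrence of 30% within three months of treatment (Section I.2). All other inputs below are labelled as assumptions.

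**1. The floor.** Change = later score − baseline score. With baseline 0 and a minimum score of 0, change is 0 or more. The best preventive result is exactly 0, and every negative contribution to the mean comes from women with a baseline above 0.

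**2. Dilution.** Let f be the share starting at 0 and D the mean fall in the others. If the women at 0 stay there, the pooled fall is (1 − f) × D. For D = 3 points (assumption):

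| f (assumed) | Pooled fall | Reduction |
|---|---|---|
| 25% | 0.75 × 3 = 2.25 | 25% |
| 50% | 0.50 × 3 = 1.50 | 50% |
| 75% | 0.25 × 3 = 0.75 | 75% |

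The percentage reduction equals f whatever D is. Any relapse among women starting at 0 shrinks the pooled fall further.

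**3. Pooled change with no gel effect.** At a constant rate (assumption), 30% in three months gives 1 − 0.7^(1/3) = 11.2% at one month. Assume that symptomatic women score 8 on the full survey, that a share q of them resolve to 0 unaided, and that 11.2% of women at 0 relapse to 8. The mean change at the end of the intervention is −(1 − f) × q × 8 + f × 0.112 × 8.

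| f | q = 25% | q = 50% |
|---|---|---|
| 25% | −1.50 + 0.22 = −1.28 | −3.00 + 0.22 = −2.78 |
| 50% | −1.00 + 0.45 = −0.55 | −2.00 + 0.45 = −1.55 |
| 75% | −0.50 + 0.67 = +0.17 | −1.00 + 0.67 = −0.33 |

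Under these assumptions the entry mix and unaided resolution alone move the result from a slight rise to a fall of almost 3 points.

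**4. What the symptom-free group can show.** At two months (about collection 3) the same rate gives 1 − 0.7^(2/3) = 21.2% relapsing, so 78.8% stay at 0 with no gel effect. If all n stay at 0, the exact 95% lower limit is 0.025^(1/n).

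| n of 20 at 0 | Expected relapses, no gel effect | Chance of none, 0.788^n | Lower limit if all stay at 0 |
|---|---|---|---|
| 5 | 1.1 | 30% | 48% |
| 10 | 2.1 | 9% | 69% |
| 15 | 3.2 | 3% | 78.2% |

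Even a perfect result leaves 78.8% inside the interval in each case. This group's result can describe, but it cannot establish prevention.

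**The case against.** A reader might infer two stronger statements. The documents support neither.

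- *Women in remission cannot succeed.* There are two primary outcomes, and they can still gain on lactobacilli. On symptoms the floor binds only at a score of exactly 0. Survey B also asks about worry, appearance, frustration, embarrassment and intimacy, which may be positive between episodes. How many women will start at 0 is unknown.
- *Any gain is a treatment effect.* With no control group, a fall may equally be natural resolution, regression to the mean or the after-effect of a recent course. Nor does having symptoms establish active BV or candida, since no test at entry is described.

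Other objections carry weight. Mixed entry is open and deliberate: Section IV.4 names both prevention and resolution as possible benefits. The formal outcomes in Section I.1 do not use the word prophylaxis, and the study is a 22-woman pilot. The magnitudes above are largely assumed, and the 30% figure is for BV after treatment, not for candida or for women not recently treated. Reporting by subgroup is often left to a statistical analysis plan, which is not shown here.

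These points limit the size of the problem and rule out the stronger wording. They do not remove the mismatch. The prophylaxis aim, the mixed entry and the direction of the primary outcome are all fixed in the protocol, and an analysis plan should not redefine a primary outcome.

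**Conclusion.** The concern holds in a limited form. As defined, the symptom primary outcome cannot register prevention in a woman who starts at 0, and a pooled decrease is not evidence of prophylaxis. That much follows from the scoring and needs no assumption. Its numerical weight does: the pooled fall is smaller than the fall in symptomatic women by the share starting at 0, so 25% to 75% smaller if that share is 25% to 75%, provided those women stay at 0. The lactobacillus outcome remains open to all women. There the baseline matters in a softer way: a woman who already has a lactobacillus-dominated community has less room for an increase, and the rationale in Section I.2 concerns CST 4.

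**What to change.** Keep eligibility and the pooled analysis, and add the following to Section III.2:

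1. Define baseline status by the baseline Survey B items 1–7 score alone: 1 or more is symptomatic, 0 is symptom-free. Do not use an episode noted at recruitment. A woman treated since then may score 0, and she would be placed in the group expected to decrease.
2. In symptomatic women, report the change from baseline. In symptom-free women, report the proportion still at 0 on items 1–7 at collections 2 and 3, with confidence intervals.
3. Read new burning or itching against the side-effect entries in the diary (Appendix E). Appendix F lists burning in 18.0% and pruritus in 14.5% of users, and these overlap with Survey B items 2 and 1. The diary covers the intervention period, so it helps mainly at collection 2.
4. Show lactobacillus change by baseline CST (CST 4 versus other), which the plan already assigns.
5. State that a pooled symptom decrease does not support prophylaxis, and that the symptom-free group's result is descriptive and hypothesis-generating because there is no control.

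The cost is protocol wording; baseline Survey B, the diary and CST are already collected. The downside is small groups and wide intervals. A past-week survey at two later times also misses episodes between surveys, so remaining at 0 is not the same as freedom from recurrence.
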